- What features and functionalities could better help you support patients throughout their treatment? What information do you see as critical to provide to TB patients throughout their treatment? What functions would facilitate you managing a large patient cohort effectively? What name would you recommend for the app?

Method and analysis: All focus group sessions and interviews will be audio-recorded and transcribed verbatim for analysis. Identified glitches, feedback, recommendations will be synthesized for programmers. Steps will be repeated after refinements made.

Aim 3. Assess feasibility, usability, perceived usefulness, and initial efficacy of the resulting product in a pilot RCT. By conducting a pilot RCT, mimicking all of the major essentials of definitive trial, I will determine the feasibility, usability, perceived usefulness, and further refine intervention in congruence with iterative framework and estimate effect size for a future definitive evaluation. The goal is to increase TB treatment success rates to WHO minimum 85% target and reduce rates of poor outcomes (e.g., default, drug resistance).

Sample size: To detect a 15% increase in treatment success with 80% power and an α of 0.05 (two-tailed) a sample size total of 348 is required. Based on recommended sample size calculations for pilot RCT,⁵⁶ 9% of sample size of main planned trial is needed, 35 participants. The power calculation is only applicable to the primary outcome of treatment success and not for the subgroup analyses. To be cautious and account for an estimated 20% attrition, the recruitment target was increased to 46.

Setting: Health Region V described above.

Recruitment: All patients newly diagnosed with TB meeting inclusion criteria will be notified of the study by clinic staff and referred to research staff to receive full explanation and have questions answered. Signed informed consent will be obtained for all participants. A recruitment log will be maintained to document screened patients and reasons for declining participation. Patients will be enrolled on an ongoing basis, and recruitment is estimated to be completed in 4 months after start of recruitment.

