Inclusion/Exclusion criteria: Patients 18 years of age or older starting TB treatment for the first time, with no known TB drug resistance, HIV negative, owning or having regular access to a smartphone, and who are able to operate the mobile phone to communicate or have someone able to assist. Excluded will be patients who are severely ill (i.e., requiring hospitalization) or reside in the same household with another study participant. Patients with known drug resistance and those with HIV co-infection will be excluded because their care is managed separately and the treatment regimens and duration differ. Screened patients who do not meet study eligibility will have specific screening data (including gender, age and reason for exclusion) entered into the study database which data will be helpful in examining the patient population and feasibility of enrollment criteria.

Randomization: Participants will be randomized to usual care and usual care plus app-based intervention at a ratio of 1:1 in blocks of 10 to ensure balanced representation in both arms. Random allocation sequence will be generated using <http://www.randomization.com/>. Opaque envelopes sequentially numbered and sealed will be used for treatment allocation concealment. Due to the nature of the intervention, blinding to the group allocation cannot be achieved for research staff. Clinicians will not be made aware of the group allocation unless their patient informs them.

Usual care: Drug treatment and patient monitoring are provided free of charge in the public health system. Usual care consists of outpatient treatment management from the time of diagnosis (unless symptoms are severe and hospitalization is recommended), routine clinical and laboratory tests, and follow-up appointments determined by the clinician. In general, patients receive 1-2 month's supply of medication and are asked to return monthly for follow-up appointments, or earlier if experiencing any problems. Patients with first treatment receive a 6-month regimen consisting of a two-month *intensive* phase of four drugs (rifampicin, isoniazid, pyrazinamide, and ethambutol or streptomycin), followed by a four-month *continuation* phase with isoniazid and rifampin daily or 3 times a week.⁵⁷ Three of the four medications are provided in a combined pill, therefore testing isoniazid urine metabolite is an indicator of all medications ingestion except for ethambutol.

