Outcomes: Table 5 provides an overview of primary and secondary outcomes, hypotheses, operationalization, data collection and analysis methods. **Treatment outcomes** will be measured using standard definitions set by the WHO Standards of TB treatment.⁵⁸ The primary outcome for initial efficacy will be *treatment success* based on WHO definitions: *completed* (without bacteriological confirmation) or *cured* (negative sputum smear at 6 months and at least once prior to 6 months). Other treatment outcomes include: failed (sputum smear positive at 5 months or later), died, defaulted (treatment interruption for ≥ 2 months), lost to follow-up (diagnosed, treatment outcome not documented), or transferred out (transferred to another reporting unit and treatment outcome is unknown).³² To assess **acceptability** (perceived usefulness and ease of use), we will use the Mobile Application Rating Scale (MARS).⁵⁹ The MARS has been shown to be highly reliable tool to assess app quality.⁵⁹⁻⁶¹ The scale includes three sections and a modifiable app-specific section: classification, quality and satisfaction classification section provides descriptive information about the apps. The objective app quality section includes 19-items divided into four scales: engagement, functionality, aesthetics and information quality. The subjective quality section contains 4 items evaluating the user's overall satisfaction. MARS items are scored using a 5-point Likert scale. The final MARS scores include four subscale scores, a total mean score, subjective quality score and an app-specific subscale that assesses perceived impact on the user's knowledge, attitudes, and intentions to change as well as likelihood of changing targeted behaviors. The MARS total mean score describes the overall quality of an app, while the mean engagement, functionality, aesthetics, and information quality subscale scores can be used to describe its specific strengths and weaknesses. Participants will be asked questions similar to those in Aim 2 and specifically about urine test strip use.

Table 5. Overview of variables, hypotheses, operationalization & data collection

Outcome/Variable	Hypothesis	Outcome measure	Analysis	Measurement point T0 T1 T2 T3
Primary outcomes				
Treatment outcomes	I > C success I < C other	Treatment success rate (%) Other outcomes (failed, default, died, lost to follow-up) MARS scale (Likert scale)	χ^2 test Descriptive/qualitative	X X
Acceptability*				

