Data Analysis/Interpretation: All analyses will be based on intention-to-treat. Statistical analyses will be performed using IBM SPSS, version 20 (Chicago, IL). Independent-sample *t*-tests will be conducted for continuous outcomes and chi-square test for dichotomous or categorical variables. Standard descriptive statistics of frequency, central tendency, and dispersion will be used to describe each sample. A p-value less than 0.05 will be set to detect a statistically significant difference for all analyses. I will compare group baseline characteristics including: age, gender, education, travel time to center, take other medication on a regular basis, and baseline TB knowledge. For qualitative data, the transcripts will be entered into Nvivo to organize and iteratively code using thematic and descriptive qualitative methods.^{64,65}

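### The pilot is meant to estimate an effect size, but for treatment success the plan names no between-arm effect measure and no confidence interval, only per-arm percentages and a chi-square test at p<0.05

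*Combined protocol and SAP*

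**What the plan says.** The opening paragraph of Aim 3 gives the pilot several purposes. One is to "estimate effect size for a future definitive evaluation". The Outcomes paragraph makes treatment success (completed or cured) the primary outcome for initial efficacy.

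The analysis of that outcome is described in two places:

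- The outcomes table (Table 5, Outcomes) lists "Treatment success rate (%) Other outcomes (failed, default, died, lost to follow-up" as the measure, with a chi-square test.
- Data Analysis/Interpretation, printed in Aim 3 and again under Statistical Design and Power, assigns chi-square tests to dichotomous variables and adds: "Standard descriptive statistics of frequency, central tendency, and dispersion will be used to describe each sample". It then sets the rule "A p-value less than 0.05 will be set to detect a statistically significant difference for all analyses". All analyses are by intention-to-treat.

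The Sample size paragraph, also printed twice, begins "To detect a 15% increase in treatment success with 80% power" and arrives at 348 participants. It then sets the pilot at 35 and raises recruitment to 46 for 20% attrition. It gives no power or precision for the pilot. Its sentence limiting the power calculation to treatment success does not say which trial is meant. Future Directions makes a finding that the intervention is efficacious in the pilot one condition for the next grant application, and does not define the term.

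**The concern.** An effect size for a two-arm comparison is a contrast between arms, and it is useful for planning only with its uncertainty. The plan specifies neither. Its descriptive statistics are for each sample separately, and its only between-arm result for treatment success is a p-value. The term confidence interval appears nowhere except in the title of the reference cited for the pilot's size.

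At this size a p-value is a poor summary. If the app really produced the gain that the definitive trial is designed to detect, the planned result would most often read as not significant. A reader would have nothing in the planned output to show that the data were still compatible with the target benefit, or with no benefit or some harm. At stake are the reporting and interpretation of the pilot's efficacy result and its use in planning the definitive trial. Feasibility and acceptability are analysed descriptively and are unaffected.

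**Working it through.** **Inputs from the documents.** Two-sided alpha 0.05; 80% power; a 15% increase; 348 in the main trial; 35 in the pilot, 46 recruited; 1:1 allocation; intention-to-treat.

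**Assumptions.** The control rate is not given, and 15% may be absolute or relative. Four scenarios are used:

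- 42.5% v 57.5% and 76.45% v 87.9% (relative 15%) were solved back from 348.
- 70% v 85% ends at the stated target ("The goal is to increase TB treatment success rates to WHO minimum 85% target").
- 80% v 95% has no source in the documents and serves as a favourable extreme.

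The main case is 23 per arm. It counts everyone randomised and treats default, loss to follow-up and transfer out as not success. The Outcomes paragraph lists these among the other outcomes, for example "lost to follow-up (diagnosed, treatment outcome not documented", but gives no explicit denominator rule. The second case is the 35 the plan sizes for, split 17 intervention and 18 control.

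**1. The plan's 348.** Pooled formula, per arm:

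n = [1.96·√(2p̄(1−p̄)) + 0.8416·√(p₁(1−p₁)+p₂(1−p₂))]² / (p₂−p₁)²

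For 42.5% v 57.5%: [1.3859 + 0.5884]² / 0.0225 = 3.898 / 0.0225 = 173.2, so 174 per arm and 348 in total. The relative scenario gives 173.6, also 348. For 70% v 85% the total is 242, and for 80% v 95% it is 152. So 348 can be matched, but only by supplying a control rate that the plan does not state. The 35 and 46 are taken as stated.

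**2. Power and precision of the pilot.** For every pair of success counts, the binomial probability was computed and the Pearson chi-square compared with 3.841. Power is the total probability of the pairs that exceed it. The half-width is the probability-weighted mean half-width of the 95% Newcombe interval.

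| Control v intervention | Power, 23/arm | Power with Yates, 23/arm | Half-width, 23/arm | Power, 35 evaluable | Half-width, 35 evaluable |
|---|---|---|---|---|---|
| 42.5% v 57.5% | 18% | 11% | 26 points | 13% | 29 points |
| 70% v 85% | 23% | 13% | 23 points | 20% | 26 points |
| 80% v 95% | 35% | 13% | 20 points | 26% | 23 points |
| 76.45% v 87.9% | 18% | 7% | 22 points | 15% | 25 points |

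With 23 per arm, a true target benefit is therefore labelled not significant about 65% to 82% of the time (100 − 35 and 100 − 18).

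**3. Unequal arms.** Allocation is "at a ratio of 1:1 in blocks of 10 to ensure balanced representation in both arms". Since 46 is four full blocks plus six, the arms could range from 21 to 25. Over that range uncorrected power moves by at most 6 percentage points.

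**4. What a non-significant result would mean.** With 23 per arm, when the target effect is true and the test is not significant, the upper 95% Newcombe limit still reaches the true difference in 95% to 97% of cases.

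**5. One worked result: 14/23 v 10/23.** The difference is 0.609 − 0.435 = 0.174. Chi-square = 46·(14·13 − 10·9)² / (23·23·24·22) = 389,344 / 279,312 = 1.39, p = 0.24. The Wilson limits are 0.408 to 0.778 and 0.256 to 0.632.

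- Newcombe lower limit: 0.174 − √(0.201² + 0.197²) = −0.107
- Newcombe upper limit: 0.174 + √(0.170² + 0.178²) = 0.420

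The planned output is two percentages and p = 0.24. The informative statement is +17 points, 95% CI −11 to +42.

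**The case against.** The plan commits to an effect size, reports a success percentage for each arm and does not forbid an interval. Anyone can subtract the percentages, so no data are lost. This stands, and it limits the point: what is missing is a named measure and its precision, not the underlying information.

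Three stronger readings are tempting and go beyond the documents.

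- *That p<0.05 decides whether the grant application goes ahead.* Future Directions leaves efficacious undefined and does not tie it to the p-value.
- *That the pilot will overstate the benefit.* Among favourable significant results, the mean estimate is about 1.7 to 2.4 times the truth with 23 per arm, and up to about 2.8 times with 35 evaluable. This applies only if significant results are singled out, which the plan does not state. Adding an interval would not shrink such an estimate, though it would show its uncertainty. It is a secondary caution.
- *That the plan claims 80% power for the pilot.* The paragraph contains one power calculation, tied to 348 and to the main trial, and a careful reader can attribute it correctly. The sentence needs clarifying but is not a false claim.

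It is also fair that the power figures depend on assumed rates, and that the most favourable one (35%) comes from a scenario without a source. The two scenarios that reproduce 348 both give about 18% with 23 per arm. Finally, the analysis column of the outcomes table is broken in the extracted text, but Data Analysis/Interpretation separately assigns the chi-square test to dichotomous variables.

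**Conclusion.** The point holds. The stated estimation aim has no matching analysis: for treatment success the plan names no between-arm measure and no interval, and its only inferential result is a chi-square test at p<0.05. Under the assumed scenarios that test has about 18% to 35% power with 23 per arm and 13% to 26% with 35 evaluable. With Yates correction and 23 per arm it has 7% to 13%.

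The main harm is the missing precision. The difference will typically carry a 95% half-width of 20 to 26 points (23 per arm) or 23 to 29 points (35 evaluable), and nothing planned would show it. The conclusion does not depend on which scenario is right, only the size does. It should be fixed because the remedy is cheap and serves the pilot's own aim. It does not threaten the conduct of the trial.

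**What to change.** **Outcomes table and both copies of Data Analysis/Interpretation.** For treatment success, write: *The primary efficacy result of the pilot is the difference in treatment-success proportions (intervention minus control) in all randomised participants, with a two-sided 95% confidence interval by a small-sample method such as Newcombe. The chi-square p-value is descriptive only. A non-significant result is not evidence against efficacy.* State there how a transfer with unknown outcome is counted. Another small-sample interval method would also serve, provided it is named in advance.

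**The p<0.05 sentence, both copies.** Amend it to exclude treatment success. Left as it is, its reference to all analyses would contradict the new text.

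**Sample size, both copies.** Add: *The 80% power applies only to the 348-participant trial. The pilot is not powered to test efficacy.*

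**Future Directions.** State that efficacy in the pilot is judged from the estimate and its interval, not from p<0.05.

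**Cost.** Wording only, with no extra participants or data. The Newcombe interval is closed-form from the four cell counts, so it can be computed outside SPSS if needed. The downside is that the pilot gives no yes/no verdict on efficacy and the reported interval will be wide.

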Program evaluation		Feasibility, ease of use, home drug metabolite testing, recommendations	Descriptive/qualitative	X
Secondary outcomes				
Global Health PROMIS SFv1.1	I>C	CDE outcome for self-management		X X
WHOQoL-BREF measures				
Level of engagement*		# of messages: notification, side effects, questions	Descriptive	X X X X
TB knowledge	I > C	Change in TB knowledge score	t-test	X
Appointment attendance	I > C	Mean proportion	χ^2 test	X X X
Cost accounting		Log of intervention costs	Descriptive	X X X X
Subgroup analyses				
Gender	Female>male			
Age	Older>younger			
Mobile phone access type	Personal>shared			
Time to clinic	$\leq 30 > 30$ min		χ^2 test	

Note: I=intervention, C=control; PROMIS= Patient-Reported Outcomes Measurement Information System; CDE=common data elements; T0 Screening, T1 Baseline, T2, 2 months, T3 6 months, * = data collected from intervention group only

Secondary outcomes include the Global Health Patient-Reported Outcomes Measurement Information System (PROMIS) short form,⁶² TB knowledge, level of tool engagement, appointment attendance and cost accounting. The Global Health SF is a recommended outcome measure for self-management, includes 10 items, is available in the Spanish language, and can be integrated into REDCap. TB knowledge will be assessed using items from the Tuberculosis Knowledge Assessment Questionnaire at pre and post-intervention.²⁵ Items include questions focused on exploring knowledge about: causes and symptoms of TB (5 items), TB transmission (4 items), TB treatment (2 items), and TB prevention (5 items)(Appendix C). The questions are structured to answer (yes, no, I don't know). For those randomized to app, I will evaluate the level of engagement with the intervention (e.g., percentage of notification without a reminder, number of questions, number of reported side effects).

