Recruitment: There are over 10,000 new TB cases per year in Argentina, half of which are identified in the Province of Buenos Aires. Health Region V had 1020 cases in the last analyzed cohort. During recruitment phase, in the event that there are insufficient number of subjects, I will enroll additional study sites such as another regional public hospital with the assistance of onsite co-mentor [name]. He recently completed a prospective cohort study recruiting from 47 different healthcare facilities from 16 different departments. The proposed study will take place at one large public hospitals where there is a higher concentration of cases. **IT logistics:** Refining and adding features to an open-source software is realistic and achievable. Given [name] (co-mentor) experiences with successfully implemented apps and international mHealth interventions, he will supervise the IT component of app refining, implementation and trialing.

Timeline: Table 6 provides timeline of the proposed research activities under this award.

Table 6. Timeline of Proposed Research Activities

Future Directions: If intervention is found to be feasible, acceptable, and efficacious in pilot RCT, a subsequent R01 application will propose a comparative effectiveness evaluation comparing app to mixed strategies and directly observed therapy. The ultimate goal is to plan for a sustainable, scalable, and easily adaptable intervention managed by local healthcare teams. Because of a significant percentage of foreign born TB cases in the US originated from a Spanish speaking country the intervention could be trialed in other Spanish speaking settings where treatment support is limited or could be adapted for latent TB infections in the US (with rates of abandonment over 50%)⁶⁶ or other chronic or long term treatment regimens where patients self-administer, have poor adherence, and limited treatment support.

Activity	Year 1		Year 2		Year 3	
	1	2	3	4	5	6
6month increments						
Coursework						
Aim 1						
Aim 2						
Aim 3						
Analysis						
Submit R01						
Result dissemination						

Statistical Design and Power

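### An unadjusted p<0.05 rule covers every analysis, about 13 to 19 comparisons including, by implication, six at baseline; it should apply to treatment success only

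*Combined protocol and SAP*

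**What the plan says.** The Data Analysis/Interpretation section appears twice, under Aim 3 and again under Statistical Design and Power. Both copies say: "A p-value less than 0.05 will be set to detect a statistically significant difference for all analyses". Both assign t-tests to continuous outcomes and a "chi-square test for dichotomous or categorical variables". The next sentence in both is: "I will compare group baseline characteristics including: age, gender, education, travel time to center, take other medication on a regular basis, and baseline TB knowledge". That sentence names no test.

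The outcomes table (the second of the two tables numbered 5) gives the treatment-outcome hypotheses as "I > C success I < C other". It lists PROMIS, TB knowledge and appointment attendance with hypotheses favouring the intervention, WHOQoL-BREF with neither hypothesis nor test, and four subgroup analyses.

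The Outcomes text names treatment success as the primary measure of initial efficacy. The Sample size text says that the power calculation does not extend to the subgroups. Future Directions makes the next grant application conditional: "If intervention is found to be feasible, acceptable, and efficacious in pilot RCT". It gives no criterion for the last of these three conditions. The documents contain no multiplicity adjustment, no order of testing and no statement that any test is exploratory.

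**The concern.** A single threshold for everything gives a subgroup or secondary result the same standing as the primary comparison. Someone following the plan as written could call any result with p<0.05 statistically significant, and nothing in the analysis section would mark it as unprotected. The decision about the next trial rests partly on efficacy, so the status of such a result should be settled beforehand.

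The baseline comparisons are a separate matter. Allocation is random and concealed in sealed, numbered envelopes (Randomization section). Any difference between arms at baseline is therefore due to chance, and the null hypothesis is true by design. A significant result says nothing about the patients. A non-significant one, at about 23 per arm (46/2), does not show that the arms are alike.

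**Working it through.** The plan states no overall error rate, so there is no figure of its own to reproduce. The inputs are the per-test level of 0.05 (Data Analysis/Interpretation) and a count of comparisons from the outcomes table and the baseline list.

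**Count**

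- Treatment success: 1
- Other treatment outcomes, taken together: 1
- PROMIS: 1 (the analysis cell is blank, so the default t-test is assumed)
- TB knowledge: 1
- Appointment attendance: 1
- Subgroups: 4 (gender, age, phone access, time to clinic)
- Named baseline characteristics: 6

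The total is 1 + 1 + 1 + 1 + 1 + 4 + 6 = 15. It depends on how the table is read:

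- Low: 15 − 2 = 13. This drops the other outcomes, which taken together are nearly the complement of success. It also drops PROMIS, because the exit survey that contains it is described for the intervention arm only.
- High: 15 + 1 + 3 = 19. This adds WHOQoL-BREF and splits the four categories in "Other outcomes (failed, default, died, lost to follow-up" into separate tests. Testing attendance at each of its three marked time points would add more.

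**Formulae**

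For k tests with every null true, the expected number of false positives is 0.05k, whatever the correlation. If the tests are also independent, the chance of at least one is 1 − 0.95^k.

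| Set | k | Expected | Chance of at least one |
|---|---|---|---|
| Outcome and subgroup comparisons beyond treatment success | 8 | 0.40 | 1 − 0.6634 = 33.7% |
| The same with treatment success | 9 | 0.45 | 1 − 0.6302 = 37.0% |
| Baseline only | 6 | 0.30 | 1 − 0.7351 = 26.5% |
| All, low count | 13 | 0.65 | 1 − 0.5133 = 48.7% |
| All, middle count | 15 | 0.75 | 1 − 0.4633 = 53.7% |
| All, high count | 19 | 0.95 | 1 − 0.3774 = 62.3% |

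**Sensitivity to the assumptions**

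- Correlation: with every pair of tests correlated at 0.3, nine tests give 32.5% and fifteen give 45.9%. At 0.5 they give 26.9% and 36.2%.
- A simulation with 23 patients per arm and all nulls true used t-tests and uncorrected chi-square tests. Correlation among outcomes was 0 to 0.6, and WHOQoL-BREF took the place of the other treatment outcomes. It gave about 34% to 37% for nine outcome and subgroup tests, and 52% to 55% once the six baseline tests were added.
- Fewer true nulls: if the five hypotheses comparing the arms are all correct, 15 − 5 = 10 nulls remain, and 1 − 0.95^10 = 40.1%. Without the baseline six, four remain, and 1 − 0.95^4 = 18.5%.

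**The case against.** A reader might infer that a false significant finding is more likely than not. The documents do not support this. The figure passes one half only if the baseline comparisons are counted, at least 14 tests are performed (1 − 0.95^14 = 51.2%), every null is true and the tests are independent. A baseline p<0.05 is also not a false efficacy finding. This objection stands in full.

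A reader might also infer that efficacy has no defined endpoint, so that any secondary result could serve. The Outcomes section names treatment success, and the power calculation is tied to it alone. What remains is narrower: the significance rule is not confined to that endpoint, and Future Directions sets no criterion. For the three secondary outcomes with a hypothesis favouring the intervention, the chance of any p<0.05 is 1 − 0.95^3 = 14.3%, and about 7% in the favourable direction (1 − 0.975^3 = 7.3%).

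The subgroup hypotheses, as written, compare kinds of patient (female above male, older above younger) rather than arms. Their nulls are not true by design, and a positive result need not be a false efficacy claim. That also stands, and the percentages are therefore conditional on the nulls being true.

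Baseline testing is inferred. The baseline sentence names no test, the t-test is assigned to outcomes, and descriptive statistics are also promised. But the sentence directly follows a rule for all analyses, and the chi-square test is assigned to variables rather than only outcomes. Nothing in the documents says that a chance imbalance would be reported as failed randomisation.

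The small sample does not drive the error rate; it affects power, which is a different question. Finally, this is a pilot, and the labelling of non-primary results is partly a matter of reporting. That limits the weight of the point but does not remove it, because the plan states a significance rule and gives it no limit.

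**Conclusion.** The point holds in a limited form. An unadjusted p<0.05 rule applies to about 13 to 19 comparisons, without hierarchy or exploratory label. If all nulls are true and the tests independent, the chance of at least one p<0.05 is 34% for the eight non-primary outcome and subgroup comparisons and 37% with treatment success added. It is 26% for the six baseline comparisons alone and 49% to 62% for everything. These are upper-end figures for each count, since correlation or real effects would lower them.

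The total for all comparisons mixes families with different consequences and should not be quoted as the risk of a false efficacy claim. If the baseline comparisons are tested, the tests are uninformative whatever the count. This is an inexpensive improvement to the plan rather than a fault in the design.

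**What to change.** In both copies of Data Analysis/Interpretation, replace the threshold sentence with text to this effect: a two-sided p-value below 0.05 will be used for the comparison of treatment success between arms only; other treatment outcomes, secondary outcomes and subgroup analyses are exploratory and will be reported as estimates with 95% confidence intervals, without claims of statistical significance; baseline characteristics will be described by arm (means and standard deviations, or counts and percentages) without tests.

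The text should add that an exploratory interval excluding no difference is not to be read as a significant result, since otherwise the same test returns in another form.

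The edit is short, is made in two places and needs no new data. It suits the pilot's stated aim of estimating an effect size. The one loss is that secondary and subgroup results can no longer be called statistically significant.
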